the prior three months, to exclude subjects on special diets (e.g., vegetarian, gluten-free) and recruit individuals who meet criteria for a typical American diet consisting of daily fiber  $\leq$  16 grams and daily saturated fat  $\geq$  11 grams. All subjects will be  $\geq$  21 years old [expected to be over 50 years old because of a history of polyps], and will be recruited after reviewing the endoscopy database of Rush University's Gastroenterology Division. Exclusion/inclusion criteria, definition of AUD and advanced adenoma are described in Human Subjects. Subjects are asked to avoid any alcoholic drinks for one week prior to each study. One week prior to the study, subjects complete the food/sleep questionnaire/(FSQ) (see Human Subjects) to record baseline food/sleep patterns. Sleep patterns will also be recorded by wrist actigraphy (Actiwach 2, Phillips Inc.). Each subject will undergo four conditions (each for one week in duration with a week wash-out in between [Fig 7]. The order of experiments will be randomized [concealed randomization]. A 24h food recall will be completed by participants using ASA24 at baseline and once during each intervention. This will be used to both determine that dietary intake is kept constant throughout the study, but also to verify time of eating on the FSQ in each of the treatment periods. "Right-time eating" is defined as breakfast (no later than 8am), lunch (no later than 1pm) and dinner (no later than 6pm), while "delayed eating" will be applied by delaying each meal by 3h. The choice of 3h is based on prior reports that alteration in the meal time for 3h can affect weight. Subjects will continue their regular energy and macronutrient content. All attempts will be made to keep sleep-wake periods constant between 11pm and 7am  $\pm$  2 hours. The limit of 2 hours was selected because sleep/wake periods over 2 hours would lead to disrupted circadian rhythms. Adherence to the protocol will be monitored via the FSQ. Subjects will enter the Biological Rhythms Research Lab after each week of the intervention period for 24h for assessments of central circadian rhythms (hourly salivary melatonin) and peripheral clock genes of the digestive tract from mucosal cells taken from buccal swaps once every 2h (12 time points). Extracted cells will be analyzed for expression levels of clock genes (*Per2*, *BMAL1*, *Clock*, *Cry1*, *Reverb-alpha*, *ROR-alpha*). While frequent endoscopic sampling of the intestine is not practical in humans, frequent buccal sampling is the most feasible method to assess the intestinal circadian rhythm^86. Further, using buccal sampling is an acceptable method to assess the digestive tract rhythm, as the intestinal cells have common zeitgebers (SCN, food and GI hormones). Nonetheless, we will also collect rectal swab every 12 hours (2 time points; first sample at the time of sigmoidoscopy) to validate that buccal sample represent disruption of digestive tract circadian rhythmicity by delayed eating. Our prelim data show feasibly of RNA analysis of clock genes from rectal swabs (Fig 8). The observed reciprocal RNA expression of the clock positive limb (*Bmal1* and *Clock*) vs. negative limb (*Per2* and *cry1*) members is suggestive of an expected anti-phasic pattern. Rectal swab sampling more than twice is not practical. Although the rhythm of proximal part may phase-advance the distal part of the digestive tracts, rhythm of different segments of GI tracts are still in synchrony to maintain a healthy physiologic homeostasis. Therefore buccal rhythm, though not a direct predictor of colonic rhythm, fits our purpose of assessing alteration of digestive tracts rhythm of subjects in response to our intervention (alcohol or food timing). For alcohol-related experiments, subjects will be given bottles of red wine and asked to drink wine with dinner (0.5 g/kg) for the week prior to the Lab visit. We have shown that this protocol causes disruption of circadian genes in PBMC [Fig 6] and promote systemic inflammation (unpublished data). To increase compliance, each subject is given enough bottles of wine to share with his/her partner at dinner.

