Therefore we use FFQ at inclusion to minimize dietary variability among subjects. Prior reports indicate that individuals maintain a consistent dietary pattern over time and compensate for changes in energy intake over the short-term. Thus, it is expected that the subjects during our study period will maintain a consistent pattern of intake. In addition, the potential effect of the differences in energy and macronutrient intake at various time points throughout the day will be mitigated by the use of the cross over design. Further, we collect dietary composition data during the study period which will be used for post-hoc analysis of the potential modulating effect of type of diet on alcohol-induced effects. We selected a one-week period for each intervention as this time is sufficient to see changes in circadian rhythms in response to alcohol [Fig 6], and food [Fig 2]. However we will re-evaluate this time selection following the first six subjects, and if, in the unlikely event we do not see any clear evidence of dyssynchrony, we will increase the intervention time to 10 days. One-week wash-out should also be sufficient to see the recovery from each intervention. Likewise, after the first six subjects, we will see if the wash-out period is adequate; if not, we will increase wash out times to 10 days. We will recruit 44 patients per our calculated sample size (see below). We plan to recruit 55 subjects, assuming 20% drop out (due to the length of the study). In our cross over study, every case acts as its own control, eliminating the need for large sample sizes that would have been required to account for inter-individual heterogeneity. Human circadian studies have a smaller sample sizes due to multiple time point data obtained for every subject, and the intensive nature of the protocol like ours with four of 24hr phase assessments in the Lab where subjects are kept awake. Indeed, a highly cited circadian study reported their findings with n of 5.

**Aim 3: To determine how disruption of circadian homeostasis by delayed eating promotes alcohol-induced colon carcinogenesis in susceptible subject.**

[figure not shown]

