
**Statistics and Overview of data analysis.** A sample size of 44 achieves 81% power to detect 0.1 mean changes in circadian rhythm profiles measured by melatonin and circadian gene expression and changes in immune gene expression and carcinogenesis markers (proliferation, apoptosis and DNA markers) within a subject with an estimated standard deviation of differences of 0.3 under a significance level (alpha) of 0.05 using a two-sided paired t-test. Power will be increased by using multivariable regression including other covariates that may affect the outcomes including demographics such as gender, BMI, age, race and chronotype. Repeated Measure ANOVA with two factors (alcohol, eating pattern) and their interaction (alcohol\*eating) will be used. To control various types of additional predictors other than alcohol and eating conditions, a Generalized Estimating Equation (GEE) model approach will be used.

**I. Generation of immune profiles in response to alcohol and abnormal food timing:** In Aim 1, RNA-seq, will be done to infer Treg/Th17/neutrophil profiles, associated with worsening polyposis in response to alcohol and abnormal eating patterns (or each alone). The immune signature will be used for profiling the gene expression data from mucosal biopsy tissues obtained in Aim 3a.

**II. Immune profiling from sigmoid tissue:** In Aim 3a, RNA-seq will be done on biopsies followed by immune profiling using CIBERSORT. Immune signatures determined in Aim 1a will be used as a guide to interrogate the profiles obtained from endoscopic sampling in response to alcohol or delayed food timing, or both.

**III. Microbial composition and structure:** 16S rRNA amplicons will be sequenced using an Illumina MiSeq instrument, with an anticipated output of 50,000 sequences per sample. The surveys of microbial genes generated by deep-sequencing will be used for microbial composition profiling using the Bioconductor R package metagenomicSeq and diversity analysis with the Shannon’s index using the

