#### **Diet and sleep assessments:**

Although the primary aim of this study is not to see the effect of type of diet on our outcomes, it is possible that the type of food affects the circadian rhythm, immune response and microbiota and eventually the measured carcinogenesis markers. Therefore, to decrease diet variability of subjects, we will use a validated food frequency questionnaire (FFQ) to assess dietary habits over the prior three months, to exclude subjects on special diets (e.g., vegetarian, gluten-free) and recruit individuals who meet criteria for a typical American diet consisting of daily fiber  $\leq$  16 grams and daily saturated fat  $\geq$  11 grams. We will use the ASA24, a standardized 24h food recall questionnaire, which will be completed by participants at baseline and during each intervention, prior to each study visit. This will be used to determine whether dietary intake is kept constant throughout the study.

In addition we will use a structured, IRB-approved questionnaire (FSQ) that was developed by our group to assess the timing of food intake as well as alcohol consumption. The time of eating obtained from the FSQ will be verified by the ASA24, a standardized dietary assessment tool. The FSQ also assesses sleep patterns. The sleep pattern will be further verified by Sleep patterns recorded by wrist actigraphy (Actiwach 2, Phillips Inc.). FSQ, ASA24 and wrist actigraphy will monitor adherence to the protocol.

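### The promised power gain from gender, BMI, age, race and chronotype does not follow: entered as additive terms, these covariates cancel from the within-subject contrasts

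*Protocol*

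**What the plan says.** The paragraph on statistics and overview of data analysis, at the end of C. Approach, sizes the trial with a two-sided paired t-test: 44 subjects, a mean change of 0.1, alpha 0.05, and change measured "within a subject with an estimated standard deviation of differences of 0.3". The stated power is 81%. It continues: "Power will be increased by using multivariable regression including other covariates that may affect the outcomes". The examples it gives are five characteristics of the subject: gender, BMI, age, race and chronotype.

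Two analysis models follow. The first is "Repeated Measure ANOVA with two factors (alcohol, eating pattern) and their interaction". The second is a GEE, introduced with "To control various types of additional predictors other than alcohol and eating conditions". Neither names period, although Aim 2 (Methods) gives each subject four one-week conditions in randomised order.

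The data that vary between periods have other stated uses. In Aim 2 (anticipated results), "we collect dietary composition data during the study period which will be used for post-hoc analysis of the potential modulating effect". Under Diet and sleep assessments, "FSQ, ASA24 and wrist actigraphy will monitor adherence to the protocol".

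Two other places bear on sex. Aim 2 (Methods) fixes 22 men and 22 women, and section 4.1.1(a) expects that men and women may respond differently to eating pattern and alcohol.

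**The concern.** In a crossover each subject is their own control, as Aim 2 itself says. Stable differences between people are therefore already absent from the comparison. A covariate that only explains such differences has nothing left to explain in the within-subject contrast. The protocol nevertheless presents these covariates as a certain source of extra power.

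What is at stake is limited. A reader may treat the sentence as a reserve against optimistic planning assumptions, and with the named covariates entered additively there is no such reserve. No sample-size figure depends on the sentence.

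The second and lesser matter is that the repeated-measures model written out leaves period among the residual variation. If outcomes drift over the four visits, the standard errors are larger than they need be.

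**Working it through.** **Inputs from the protocol.** n = 44, mean change 0.1, SD of differences 0.3, two-sided alpha 0.05, four conditions per subject, 55 recruited with 20% dropout. ICC, covariate strength, missing fractions and period drift are not given; they are assumptions below.

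**1. The plan's own figure.** Noncentrality = 0.1/0.3 × √44 = 2.21 on 43 df, which gives 58% power, not the stated 81%. That mismatch is a separate matter, and the present point does not rest on it.

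**2. Why additive terms cancel.** Write the outcome of subject i under condition j as Y_ij = s_i + β′x_i + τ_j + e_ij, where x_i holds the subject's covariates. Then

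Y_ij − Y_ik = (τ_j − τ_k) + (e_ij − e_ik).

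Both s_i and β′x_i drop out. The SD of the difference, and hence the power, is the same with or without x_i. Alcohol, eating and alcohol*eating are all contrasts of this kind.

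**3. Check with complete data.** In simulated trials of 44 subjects × 4 conditions with five subject-level covariates, exchangeable GEE gave an SE ratio (with/without covariates) of 1.000 for all three terms. Estimates differed only by rounding error, about 1e-16 or less. For the simple alcohol contrast the SE was 0.0447 and simulated power 61.0%, both ways.

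**4. Check with missing periods.** Assumptions: ICC 0.3 to 0.8; covariates explain 25 to 50% of between-subject variance.

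| Data | SE with / without covariates |
|---|---|
| 55 recruited, 20% dropout | 0.998–1.000 |
| 20% of subject-periods missing | 0.995–0.999 |
| 40% of subject-periods missing | 0.986–1.000 |

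The last row is relevant because section 4.1.1(a) makes the 24-hour circadian assessment optional. Even there the gain is at most 1.4%.

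**5. Where a gain could arise.** Regressing the change on sex is equivalent to a sex-by-condition term. If sex explains a share R² of the variance of the differences (assumption), the residual SD is 0.3 × √(1 − R²), with 42 df:

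| R² | Reduction in SE | Power for 0.1 (58% without) |
|---|---|---|
| 5% | 2.5% | 60% |
| 11% | 6% | 63% |
| 20% | 11% | 68% |

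The 11% row corresponds to an effect of 0.2 in one sex and 0 in the other: variance 0.1² = 0.01, and 0.01/0.09 = 11%.

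A period-varying covariate not shifted by the conditions also lowers the SE by the factor √(1 − R²), where R² is now its share of the within-subject variance: 2.5, 5 or 11% for 5, 10 or 20%.

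**6. Period.** Assuming equal, independent within-subject errors, the within-subject SD is 0.3/√2 = 0.212. The main-effect SE in the factorial model is 0.212/√44 = 0.0320 on 129 df, giving 87% power for 0.1. With random order and an assumed linear drift per period:

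| Drift per period | SE without / with period | Ratio |
|---|---|---|
| 0 | 0.0319 / 0.0323 | 0.99 |
| 0.02 | 0.0322 / 0.0323 | 1.00 |
| 0.05 | 0.0333 / 0.0322 | 1.03 |
| 0.10 | 0.0374 / 0.0323 | 1.16 |

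Main-effect power without and with period is about 84% and 86% at a drift of 0.05, and about 75% and 86% at 0.10. The mean estimate stayed at 0.099 to 0.101 either way.

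**The case against.** The strongest defence is that the protocol never says the covariates enter additively. The sentence follows a paired t-test, and the natural regression extension of that test is change regressed on covariates. There a covariate that predicts response does reduce the residual SD. The protocol expects a sex difference in response and fixes the sex split. This stands: a reader might infer that the named covariates can never help, and the documents do not support that. Step 5 shows a modest gain under assumed values. But it depends on effect modification of unknown size, the paragraph states no such term, and the claim is made without condition.

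The covariate list is also open, so period-varying diet or sleep data might be meant. That is possible, but the protocol gives those data other uses. A reader might go on to infer that the plan would adjust away part of the alcohol or meal-timing effect by using data recorded during each condition. The plan proposes no such adjustment.

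On period, the GEE sentence is broad enough to include it, and a statistical analysis plan could name it. Both are fair, and they make this part secondary. A reader might infer bias from the omission. The order is randomised, so the cost is precision only.

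Finally, a reader might suppose that the covariate gain is meant to supply part of the 81%. The protocol attributes the 81% to the paired t-test alone.

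**Conclusion.** The point holds in limited form. As additive terms, the five named covariates yield no power with complete data, and about 1% or less in standard error with missing periods over the assumed ranges. The complete-data result is algebraic and needs no assumption about covariate strength. Gains through covariate-by-condition terms or unaffected period-varying covariates are possible, but they are unspecified and their size is unknown, so the unconditional promise should not stand. No sample size, test or data collection changes as a result.

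Naming period is a worthwhile but minor improvement. Its benefit depends on drift that the documents do not quantify. It is negligible at 0.02 per period and becomes material only near 0.10, which equals the whole target effect in each period.

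**What to change.** Delete the sentence on increased power, or replace it with: *Subject-level covariates may be included, and pre-specified covariate-by-condition terms (for example sex by alcohol and sex by eating) may be added; no increase in power is assumed.*

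As a secondary change, write the repeated-measures model as subject + period (4 levels) + alcohol + eating + alcohol*eating.

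The cost is one sentence and one named model term. Period uses three degrees of freedom, about 1% in standard error if there is no drift. Sex by alcohol and sex by eating would use two more. No additional subjects, visits or data are needed.

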## 4. PROTECTION OF HUMAN SUBJECTS.

### 4.1.1 Risks to Human Subjects

#### a. Human Subjects Involvement, Characteristics, and Design

Forty-four subjects will be recruited into the study. These subjects will undergo a full history and physical examination by the PI, a licensed physician, to determine their eligibility and co-morbidities. Subjects will then sign an informed consent. In addition, subjects then fill out a questionnaire regarding their demographic data, health status, symptoms, alcohol use, dietary habits, and sleep schedule.

At baseline and prior to each study visit, subjects will complete a sleep and food diary by completing the FSQ (food timing/sleep questionnaire-attached), food frequency questionnaire (FFQ) and a standardized 24h food recall. The latter will be used to determine whether dietary intake is changed throughout the study, and to verify time of eating on the FSQ in each of the treatment periods. Subjects would also be interviewed by the PI and a clinical coordinator using the LDH assessment tool to carefully evaluate their alcohol drinking history in order to exclude subjects with alcohol use disorder (AUD). AUD will be determined according to NIAAA criteria for alcohol abuse or dependence & DSM-IV criteria for alcoholism. We will not include AUD subjects because: 1) the mucosal markers of heavy drinking could be irreversible and not comparable among different conditions of food timing and alcohol use; 2) heavy drinking is associated with multiple organ dysfunction that could independently affect CRC risk, thus exerting confounding effects; 3) heavy drinking has profound effects on sleep and circadian patterns that may not be reversible by a sobriety period of only one week. We also will exclude patients with active cancer, as cancer itself can affect the behaviors and circadian rhythm .

We will include both men and women, since we predict a possible difference between female and male subjects in response to eating pattern, and alcohol, due to known effects of gender on alcohol metabolism as well as on mucosal immunity . We will recruit patients with a history of high risk adenoma for several reasons: 1) Our preliminary data supports the synergistic effect of abnormal eating time and alcohol in a susceptible host (APC-mutant mice) and not in Black 6 mice. 2) Germline APC mutation occurs in patients harboring the trait for familial polyposis syndrome (FAP). However, this group comprise a very small portion ( $\leq 1\%$ ) of CRCs in general, and usually undergo prophylactic colectomy at an early age to prevent cancer formation. On the other hand, APC is the most frequently mutated gene in sporadic pre-cancerous colon lesions ( $>60\%$  in tubular and tubulovillous adenomas) and in cancerous lesions ( $>90\%$ ) of the colon. 3) If my study fails to show any effect of eating pattern and/food timing on alcohol's effect on colon carcinogenesis in susceptible hosts, I won't need to test this hypothesis in healthy subjects. We will include patients with a history of a conventional type of adenoma (tubular, tubulovillous and villous), which are the most common colonic precancerous lesions [with frequent APC mutations], as immediate follow up to my animal studies in APC-mutant mice. In the future, I will extend my studies to individuals with serrated adenomas, in which BRAF or KRAS mutations more commonly lead to colorectal cancer . The serrated polyps account for a minority of colorectal polyps found during endoscopy (1/5 to 1/10 of tubular adenoma rates). The distinct molecular subtypes of polyps may represent exposure to different environmental risk factors. For example, alcohol in a few but not in all studies is suggested to be associated with serrated polyps. Therefore, as an alternative strategy, and/or in my future studies, I will include patients with a history of serrated polyps.

Each subject will experience four conditions (each for one week in duration with a week +/- 2 days wash-out in between): (1) "right-time eating" / no alcohol, (2) "right-time eating" / with alcohol, (3) "delayed-eating" / no alcohol, (4) "delayed-eating" / with alcohol. The order of experiments will be randomized [concealed randomization]. All subjects will undergo unprepped sigmoidoscopy after each week of intervention. In Aim 2, all subjects will have an option to undergo a 24h circadian assessment in the Biological Rhythms Research Lab after each week of intervention. We will assess (i) central circadian rhythms by collecting hourly salivary samples for melatonin assays and (ii) peripheral rhythm in the intestinal tract by buccal swabs once every 2h (12 time points) as well as by rectal sampling twice (every 12 hr). For Aim 3, sigmoidoscopy without sedation will be used to obtain colonic samples as the safe method compared to colonoscopy, which has some small but finite risks associated with the procedure (e.g. bleeding or perforation) as well as sedation.

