**Methods:** Forty-four individuals (22 men and 22 women) with no history of alcohol use disorder [AUD] who have had advanced tubular adenoma in their sigmoid/descending colon within the last year will be recruited for a randomized cross-over experiment, testing alcohol use +/- two eating conditions on central and digestive tract circadian rhythms. To decrease diet variability of subjects, we will use a validated food frequency questionnaire (FFQ) to assess dietary habits over

[figure not shown]

**Fig 5.** Shift of central circadian rhythm, measured by melatonin profile occurs in night shift workers, and not in day workers, after moderate alcohol.

**Fig 6.** Peripheral rhythm assessed by Clock gene expression in PBMCs before (solid line) and after (dotted line) alcohol, in day & night shifters.

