#### **Subject characteristics and inclusion and exclusion criteria:**

Method: We will recruit 44 individuals (men and women) with no history of AUD (AUD = anyone meeting 2 out of 11 criteria according to DSM-5) but who have had advanced tubular adenoma in their sigmoid/descending colon within the last year into a randomized cross-over experiment. All subjects will be adults (greater than – 21 years old [expected to be over 50 years old because of history of polyps] ), and will be recruited after reviewing the endoscopy database of the Rush University Gastroenterology Department.

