#### **b. Sources of materials.**

Subjects (n= 44) will be primarily recruited from the review of our endoscopic database including all patients that underwent colonoscopy within the past year and were found to have advanced adenomas according to the American Association of Gastroenterology guidelines in their /descending colon area. The search for candidates will continue during the award period by reviewing the colonoscopy results of the patient who undergo colonoscopy at Rush Gastroenterology Department. Advanced adenoma is defined as adenomas 1 cm or greater, or with advanced neoplastic features per pathology review including presence of villous components (tubulovillous or villous), or high-grade or severe dysplasia. Patients will be contacted by a clinical coordinator and will be invited to participate in the study.

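### The protocol gives two recruitment numbers, 44 and 55, and never says that one is the evaluable number and the other the enrolled number

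*Protocol*

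**What the plan says.** The protocol gives 44 as the number recruited in five places:

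- Approach, Aim 2, Methods: "Forty-four individuals (22 men and 22 women) with no history of alcohol use disorder", described as the group to be recruited into the crossover.
- Approach, Aim 2, Anticipated results: a sentence saying that 44 patients will be recruited, with reference to the calculated sample size.
- Human Subjects, 4.1.1 a: "Forty-four subjects will be recruited into the study".
- Human Subjects, Subject characteristics and inclusion and exclusion criteria: "We will recruit 44 individuals (men and women) with no history of AUD".
- Human Subjects, 4.1.1 b, Sources of materials: "Subjects (n= 44) will be primarily recruited from the review of our endoscopic database".

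It gives 55 once, in the sentence that follows the 44 in Aim 2, Anticipated results: "We plan to recruit 55 subjects, assuming 20% drop out (due to the length of the study".

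The paragraph headed Statistics and Overview of data analysis takes 44 as the sample size for power: "A sample size of 44 achieves 81% power to detect 0.1 mean changes in circadian rhythm profiles". The SD is described as "within a subject with an estimated standard deviation of differences of 0.3", with alpha 0.05 and a two-sided paired t-test.

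**The concern.** Both numbers are attached to recruiting, so both read as enrolment targets, and only one can be. The power statement needs 44 subjects with paired data. Only the 55 leaves room for the drop-out that the protocol itself expects.

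The two numbers also sit in different parts of the document. Someone working from the Human Subjects section sees 44 and no drop-out allowance, and could close enrolment there. Someone working from the Aim 2 text would go on to 55. The split of 22 men and 22 women has the same ambiguity: it adds to 44, and nothing says whether it describes those enrolled or those evaluable.

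At stake are about nine completers (44 against 35), and the power that goes with them in a trial whose power is already modest on its own inputs.

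**Working it through.** **Inputs, all from the protocol.** Mean within-subject change 0.1, SD of differences 0.3, two-sided alpha 0.05, paired t-test and n = 44 (Statistics and Overview of data analysis). Drop-out 20% and recruitment of 55 (Aim 2, Anticipated results).

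**1. The drop-out inflation.** Enrolled = evaluable/(1 - drop-out) = 44/(1 - 0.20) = 55. The protocol's 55 reproduces exactly, which is good evidence that 44 was meant as the evaluable number.

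**2. Completers under each reading.**
- 55 enrolled: 55 x 0.8 = 44.
- 44 enrolled: 44 x 0.8 = 35.2, about 35.

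**3. The protocol's own power figure.** For a paired t-test, power comes from the noncentral t with n - 1 degrees of freedom and noncentrality (0.1/0.3) x sqrt(n).
- n = 44: noncentrality 0.3333 x 6.633 = 2.21, 43 degrees of freedom, power 58.0%. As a check, the normal approximation is Phi(2.21 - 1.96) = Phi(0.25), about 60%.
- The protocol states 81%, so its figure does not reproduce. A one-sided test does not rescue it (70.2%). Reaching 81% at n = 44 would need an SD of differences of about 0.228, or a mean change of about 0.131.

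**4. Power if only 44 are recruited.**
- n = 35: noncentrality 0.3333 x 5.916 = 1.97, 34 degrees of freedom, power 48.3%. The normal approximation gives about 50%.

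| Recruited | Completers | Power, stated inputs |
|---|---|---|
| 55 | 44 | 58.0% |
| 44 | 35 | 48.3% |

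The recruitment ambiguity costs 58.0 - 48.3 = 9.7 points. The gap between the stated 81% and the recomputed 58.0% is 23 points and exists under either reading.

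**5. Does the loss depend on the stated SD?** If the SD is set at 0.228, so that 44 completers do have 81%, then 35 completers have about 71%. The loss is again about 10 points.

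**6. Size needed on the stated inputs.** 80% power needs 73 completers. At 20% drop-out that is 73/0.8 = 91.25, or 92 enrolled.

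**The case against.** The best reply is that the document very nearly resolves this itself. The two Aim 2 sentences are adjacent, 44/0.8 is exactly 55, and the power paragraph uses 44 as its n. The same pair of sentences uses the verb recruit for both numbers, so the 44s in the Human Subjects section may be the same loose usage and not a rival target. Nothing says that enrolment stops at 44, and the recruitment plan estimates 1,375 potential candidates, so availability does not impose a cap. Most of this stands: 44 evaluable and 55 enrolled is the natural reading. But it has to be inferred. The section that describes the participants gives only 44, without a drop-out allowance, and the sex split fits only 44.

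A reader might go further than the documents allow in three ways.

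- One might infer that recruiting 44 is what loses the stated 81%, and that recruiting 55 secures it. It does not: 44 completers have about 58% on the stated inputs.
- One might infer that the Human Subjects section fixes the permitted enrolment. The protocol says only that the Institutional Review Board will approve the recruitment plan, study plan and consent form. It shows no approved ceiling and does not say which section prevails.
- One might extend the loss to the alcohol-by-eating interaction. The protocol gives no effect size or SD for that contrast, so any figure would rest on an outside assumption, and none is offered here.

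**Conclusion.** The inconsistency is real: 44 is given as the number recruited five times and 55 once, without labels that would reconcile them. The likely intent is 44 evaluable and 55 enrolled. If 44 were followed as the enrolment number, about 35 would complete, and paired t-test power would be about 48% where 44 completers would give about 58%.

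This rests on the protocol's 20% drop-out, its change of 0.1 and SD of differences of 0.3, and on counting a drop-out as contributing no paired data. A subject who leaves late may still supply some pairs, so 35 is the pessimistic end for a single comparison.

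The 81% is a separate and larger error. It is not reached under either recruitment number and should not be cited as what 55 enrolled would provide.

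**What to change.** State the same pair of numbers, 55 enrolled to obtain 44 evaluable, in each place that now gives a number: Aim 2 Methods, Aim 2 Anticipated results, section 4.1.1 a, the subject characteristics paragraph and section 4.1.1 b. Carry the 20% drop-out assumption into the Human Subjects section.

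Label the 22/22 sex split as enrolled or evaluable. If it means evaluable, equal enrolment works out at 22/0.8 = 27.5 per sex, so 27 and 28 among the 55.

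If 44 is in fact the ceiling on enrolment, keep it, say so, and restate power for about 35 completers.

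In either case, correct the power paragraph: replace the 81% with the value that its inputs give, or correct and justify the inputs. If that changes the evaluable number, the enrolled number must follow from it by the same drop-out rule.

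The cost is wording in five places and one recalculation. No participants are added beyond the 55 already planned unless the corrected power calculation leads to a larger target. If ethics approval was given for 44, the enrolment number would need an amendment; the protocol does not show which number was approved.
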